9.1.4 Study Visits 2-12

The treatment period is defined as Randomization Study Visit 1 through Study Visit 12. During the study treatment period, any AE associated with the target ulcer and all SAE of any kind will be recorded in the appropriate eCRF. Device deficiencies (DevD) will be recorded in a separate eCRF. The evaluation of all AE is described in Section 12, *Adverse Events*. All weekly visits

must be performed according to the study visit schedule (Section 17), preferably on the same day each week, to conduct all assessments and to assure compliance with treatment. A plus or minus one day visit window will be used for all study visits.

VLU subjects found to have target ulcer closure should continue the compression dressing. Appropriate treatment for DFU subjects found to have target ulcer closure is left to the Investigator's discretion. Appropriate treatment for VLU and DFU subjects, whose target ulcer is ready for and will be surgically closed, is left to the Investigator's discretion. If the Investigator believes the target ulcer is ready for surgical closure, then this procedure should be completed within the same week of the scheduled study visit. The next scheduled visit for subjects with closed target ulcers or subjects that will be surgically closed will be designated as End of Treatment Assessment Visit 14 and should occur in 7 (± 1) days.

All study procedures should occur in the order outlined in the protocol. Study Visits occurring outside the protocol specified visit window should be completed and recorded as a protocol deviation.

1. Subjects will be queried regarding any changes in general health and the use of concomitant medications.
2. Any AE associated with the target ulcer and all SAE of any kind reported since the last assessment will be recorded in the appropriate eCRF. DevD will be recorded in a separate eCRF (see "Section 12, *Adverse Events*" for reporting and evaluating AE). Also, subjects will be queried as to any additional ulcer-related interventions requiring hospital admission, surgical intervention or specialist referral since the last assessment.
3. Assess level of pain from NPWT dressing wear, since the previous study visit, using the VAS.
4. Prior to examination of the ulcer, remove compression bandaging (**for VLU subjects**) and photograph the NPWT topical dressing using the ARANZ Silhouette wound imaging and measurement device.

CONFIDENTIAL DOCUMENT

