9.1.7 Unscheduled Visits

Unscheduled exams may be conducted at the discretion of the Investigator with all obtained information recorded in the source documents and on the Unscheduled Visit pages within the Case Report Form (CRF) booklet.

Subjects using a negative pressure filler dressing or using tNPWT will be instructed to complete a dressing change in 2-3 days from application. This visit should be captured as an unscheduled visit.

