9.1.8 Concomitant Medications

A concomitant medication is any drug or substance administered from Screening Run-in Visit 1 of the study through the last study visit.

Since the ulcer treatments in this study are devices and treat only the target ulcer area covered by the device dressings, with no systemic effects, the only concomitant medications to be reported during this study in the eCRF are as follows:

- All current and past target ulcer treatments only (no doses will be recorded)
- Concomitant medications (no doses to be recorded) used to treat the target ulcer (e.g., systemic antibiotics for a target ulcer infection) and the peri-wound area (such as treatment for erythema, irritation, itching), together with the indication for the medication

- Concomitant medications used to treat all ADE, SADE, and UADE will be recorded in the appropriate eCRF forms

The use of all concomitant therapies must be recorded in the subject's source, together with any associated AE, SAE, ADE, ASADE or UADE, but only reported in the subject's eCRF as described above.

The following concomitant medications are not permitted during the study period:

- Systemic corticosteroids with daily administration of greater than 10 days
- Systemic drugs intended to function as immunosuppressants
- Any target ulcer treatment, excluding study treatment or surgical procedures, specifically intended to close the ulcer
- Topical antibiotics to the target ulcer or to the target peri-wound area
- Mid- to superpotent topical steroids used for > 10 days
- Enzymatic debriders to target ulcer
- Systemic chemotherapy
- Radiation therapy directed to the affected limb
- Current or prior normothermic (Warm-UP®) or HBO therapy within 7 days of the Screening Run-in Visit 1, unless the tissue area has been fully excised

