Duration of wear = Date of removal visit – Date of application visit – duration of study therapy interruption

If an unscheduled visit takes place between consecutive assessments multiple duration of wear values will be derived:

Duration of wear 1= Date of unscheduled visit – Date of application study visit

Duration of wear 2= Date of removal study visit – Date of unscheduled visit – duration of study therapy interruption

If more than one unscheduled visit occurs between consecutive assessments, further multiple wear times will be derived as above.

27. The average wear time per patient (patient level) will be derived as follows per subject:

Sum of duration of dressing wear (dressing level) values / Count of duration of dressing wear (dressing level) values

28. The median value for the baseline (Run-In Visit 2/Study Visit 1) target ulcer area will be derived for both the Full Analysis Set and Per Protocol populations by wound type and overall. The median value will also be derived for the depth and volume.

29. Whether or not the reference ulcer is clinically infected at any Study Visit.

30. Whether or not the reference ulcer has signs of infection at any Study Visit.

31. Whether an intervention was required will be derived for each subject:

If an unscheduled visit is recorded, where the reason for intervention is not given as routine: Intervention = Yes

If no unscheduled visits are recorded: Intervention = No

32. Whether prescription of an antibiotic was required will be derived for each subject:

If "have any systemic antibiotics been prescribed" = Yes at any assessment, or any antibiotic medications are recorded on the concomitant medications form, with a start date after randomization: Antibiotic = Yes

Document Number: 1004313

Document Version: 06

Document Part: 000

Document Status: Released

If "have any systemic antibiotics been prescribed" = No at all assessments, and no antibiotic medications are recorded on the concomitant medications form:
Antibiotic = No

33. Whether an intervention or prescription of an antibiotic was required will be derived for each subject:
If Intervention derivation (Derived Variable 31) = Yes or Antibiotic derivation (Derived Variable 32) = Yes, then need for intervention or antibiotic= Yes
If Intervention derivation (Derived Variable 31) = No or Antibiotic derivation (Derived Variable 32) = No, then need for intervention or antibiotic= No

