4.11 Exploratory Variables

Presence of Infection and Clinical signs of infection

A Fishers Exact test will be used to test for a difference in the percentage of subjects with incidence of infection presenting during the 12-week treatment period between treatments using the Full Analysis Set, the corresponding 95% confidence intervals will also be presented.

The presence of infection and clinical signs of infection will be summarized by regular Study Visit, at treatment discontinuation and, where appropriate at the one-week confirmation visit. Whether the reference wound is clinically infected at any post baseline assessment will also be summarised.

In addition, the summaries will be separated by reference wound filler used at baseline (gauze, foam or none).

Whether the reference wound has signs of clinical infection at any post baseline assessment and whether the reference wound has signs of clinical infection at treatment discontinuation will be cross tabulated against whether the reference wound has signs of clinical infection at baseline separately for each treatment.

Need for administration of antibiotics and additional interventions

A Fishers Exact test will be used to test for a difference in the percentage of subjects requiring either the administration of antibiotics or additional interventions, between treatments using the Full Analysis Set. The corresponding 95% confidence intervals will also be presented. Individually, Fishers Exact tests will be used to test for a difference in the percentage of subjects requiring the administration of antibiotics and additional interventions separately, between treatments.

The need for administration of antibiotics and additional interventions (and either intervention), and type of intervention will be summarized at per subject by treatment and wound type.

Dressing wear time

A linear regression model will be fitted to the average wear time per subject. Treatment, center, wound type, baseline ulcer area, baseline exudate level and baseline mobility level will be included in the initial model. The difference between the two treatments in terms of average wear time per subject (treatment parameter estimate) will be presented along with the 95% confidence intervals.

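### The infection flag is read only at Study Visits, which is narrower than the 12-week infection incidence that the Fisher's exact test compares

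*SAP*

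**What the plan says.** SAP 4.3 has two subject-level infection derivations. Item 29 is "Whether or not the reference ulcer is clinically infected at any Study Visit" and item 30 is "Whether or not the reference ulcer has signs of infection at any Study Visit". Neither names an unscheduled visit, an adverse event or a medication record as a source.

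SAP 4.11 applies Fisher's exact test, in the Full Analysis Set, to the "percentage of subjects with incidence of infection presenting during the 12-week treatment period between treatments". It adds: "Whether the reference wound is clinically infected at any post baseline assessment will also be summarised". It also plans infection results "summarized by regular Study Visit, at treatment discontinuation and, where appropriate at the one-week confirmation visit".

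The protocol collects infection information by several other routes:

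- Section 9.1.4 (step 2) records target-ulcer AEs and all SAEs since the last assessment, and "subjects will be queried as to any additional ulcer-related interventions requiring hospital admission, surgical intervention or specialist referral since the last assessment".
- Section 9.1.8 puts treatments such as "systemic antibiotics for a target ulcer infection" on the eCRF together with their indication.
- Section 9.1.7 provides Unscheduled Visit pages and states: "Subjects using a negative pressure filler dressing or using tNPWT will be instructed to complete a dressing change in 2-3 days from application". That contact is captured as an unscheduled visit.

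Table 17-1 marks an infection examination at both run-in visits and at Study Visits 2-12. It marks none at Visit 13 or Visit 14, and Visit 14 is also the early-discontinuation visit.

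**The concern.** The tested quantity is incidence over a period, but the flag is status at a set of weekly examinations. The two agree only if every infection is still visible at an examination that takes place and is counted.

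The narrow wording does not look like shorthand. The same SAP section separates unscheduled visits from study visits (item 26), uses unscheduled visits to define an intervention (item 31), and takes antibiotics from the concomitant medications form as well as from the visit question (item 32). Where a wider source was wanted, it was named.

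Infection incidence is a named exploratory objective and a local harm that readers will look for. Protocol 9.5 also makes statistical differences in exploratory or safety assessments the trigger for a post-hoc health economic analysis, so the result of this test can have a consequence beyond its own table.

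**Working it through.** The plan gives no infection rate, power or other figure for this endpoint, so there is nothing to reproduce. The check has three parts.

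**1. When the flag has no route to Yes**

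- *Resolved between examinations.* Visits are weekly, so an infection found and cleared between two of them is not seen at either.
- *Missed visits.* Protocol 9.2 requires discontinuation of study treatment after more than 2 missed weekly visits, so two in a row can be missed, for example in hospital. The gap is then 3 × 7 = 21 days. If the separate rule on 14 consecutive days without therapy applies first, the subject leaves through Visit 14, where no infection examination is marked.
- *After the last examination.* Study Visit 12 falls at 11 × 7 = day 77 of 84. The remaining 7/84 = 8.3% of the period has no marked infection examination. The same holds for the interval before an early exit through Visit 14. Subjects going to surgical closure also skip the examination step at that visit (Protocol 9.1.4, step 8, Note 2).

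**2. Chance that a short infection is missed**

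Assume uniform onset, an infection visible for D days, and examinations G days apart. Then P(missed) = max(0, 1 − D/G). Durations are assumptions. G = 9 is the widest gap that the ±1 day windows allow (7 + 1 + 1); G = 14 and 21 are one and two missed visits.

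| G (days) | D = 3 | D = 5 | D = 7 | D = 14 |
|---|---|---|---|---|
| 7 | 0.57 | 0.29 | 0 | 0 |
| 9 | 0.67 | 0.44 | 0.22 | 0 |
| 14 | 0.79 | 0.64 | 0.50 | 0 |
| 21 | 0.86 | 0.76 | 0.67 | 0.33 |

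An infection that leads to discontinuation for non-response has been treated for 2 weeks (Protocol 9.2). Since 14 exceeds 9, it meets at least one examination within Visits 2-12 if visits are attended.

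**3. What loss does to the test**

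This is the exact rejection probability of the two-sided 5% Fisher test with 80 per arm, by enumeration of both binomials. True infection rates and loss fractions are assumptions. With equal true rates:

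| True rate, both arms | No loss | 10% lost in both arms | 30% lost in one arm only |
|---|---|---|---|
| 10% | 0.028 | 0.027 | 0.062 |
| 15% | 0.030 | 0.030 | 0.094 |
| 20% | 0.032 | 0.031 | 0.125 |
| 30% | 0.033 | 0.033 | 0.204 |

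With true rates of 10% against 25%, power is 0.65 without loss, 0.58 with 10% lost in both arms and 0.45 with 30% lost in both. Equal loss therefore costs power and does not create false positives. Only unequal loss creates them, and the documents do not show that the loss is unequal.

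**The case against.** The strongest reply is that the documents are ambiguous rather than narrow. SAP 4.11 does not cite item 29 as the input to the Fisher test, and its own wording reaches any post-baseline assessment, treatment discontinuation and the confirmation visit. That is fair. But items 29 and 30 are the only subject-level infection derivations in SAP 4.3, so a programmer would use them. The wider wording does not help at Visits 13 and 14 either, because no infection examination is marked there.

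A second reply is that equal weekly ascertainment is a defensible choice in an open-label trial, and that adding unscheduled-visit findings may raise detection in the arm with more contacts. This stands, and it is why the scheduled-visit version should be shown as well.

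A third reply is that nothing serious disappears. Target-ulcer AEs and all SAEs are tabulated by arm, and antibiotics and interventions have their own Fisher tests. This also stands, and it limits the importance of the point. Nor is a subject with an antibiotic but no flagged infection a contradiction in itself, since item 32 accepts any recorded antibiotic. Only an antibiotic given for target-ulcer infection is informative here.

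Three stronger readings are tempting and are not supported:

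- *Every between-visit infection is scored No.* One still present at the next examined visit is counted. The only explicit No rule is the imputation for closed ulcers (SAP 2.3.5 and item 43).
- *Infections that end participation are lost.* Discontinuation for non-response normally spans a scheduled examination. The gap is limited to infections that arise after the last examination.
- *The comparison is biased between arms by a calculable amount.* PICO with filler has the same 2-3 day dressing change as tNPWT, the proportion using filler is not given, and the test compares whole arms. Filler-free PICO may also need an extra contact, since the kit limit is 6 days on moderately exuding wounds (Protocol 6.2). No text requires an infection examination at an unscheduled visit.

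**Conclusion.** The mismatch is real. Items 29-30 measure something narrower than the incidence tested in SAP 4.11, and no rule links the other records of infection to the flag. The loss is confined to infections that resolve before the next examined visit, fall across missed visits, or arise after the last infection examination.

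Its size cannot be stated from the documents. The miss probabilities depend on assumed durations and uniform onset; the error rates and power depend on assumed infection rates and loss fractions. The loss could differ by arm because mid-week unscheduled contacts are planned for tNPWT and filler users, but that is a possibility whose size and direction the documents leave open.

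The endpoint is exploratory and carries no sample size. The change is still worth making before analysis, because AE, SAE and medication records already collected can close most of the gap.

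**What to change.** For the Fisher's exact test in SAP 4.11, define Infection = Yes if any of the following is recorded with onset after Study Visit 1 and up to the end of the treatment period:

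- clinical infection at a Study Visit (including Visit 13, Visit 14 or early discontinuation), or at an unscheduled visit where it was recorded;
- a target-ulcer infection reported as an AE or SAE;
- an antibiotic whose recorded indication is target-ulcer infection.

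Present the scheduled-visit-only flag beside it, because inspection frequency can differ by arm. If the two versions disagree, readers can then see whether the added source matters.

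Reconcile items 29-30, SAP 4.11 and Table 17-1. In particular, state whether infection status is recorded at Visits 13 and 14, since SAP 4.11 plans to summarize it at discontinuation and at the confirmation visit while the table marks no examination there.

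The cost is SAP wording and one derivation. AE, SAE and medication records are already collected; the unscheduled-visit source can be used only where infection was noted on those pages. The downside is a somewhat higher reported infection rate and possibly more frequent ascertainment at unscheduled visits in the tNPWT arm. No clinical rule changes.

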Clinical signs and symptoms of infection on the target ulcer: Presence or absence of the clinical signs of infection (i.e., redness, swelling, tenderness, heat, purulence) as assessed by the Investigator or confirmed (i.e., microbiological culture) clinical infection, in the target ulcer.

Need for administration of antibiotics: Administration of antibiotics for a target ulcer infection.

Pain on removal of dressing: Subject response to the level of pain as recorded on the VAS during the removal of the NPWT dressing.

Pain on initiation of therapy/during dressing wear: Subject response to the level of pain as recorded on the VAS during the initiation of NPWT therapy (dressing draw-down) and during wear.

Dressing wear time: Time (days) between dressing changes.

Number and reason for dressing changes: Total number of dressing changes over the 12week treatment period and the documented reason for a dressing change.

Closure method: The number of subjects that undergo a surgical intervention (closure by simple flap, Split-Thickness Skin Graft (STSG), delayed primary intention with sutures).

Additional interventions: The number of subjects that require hospital admission, a surgical intervention for a wound related complication, or specialist referral for wound related complication.

Device trouble-shooting: The number and type of device trouble shooting episodes (alarm conditions/device failures/other malfunctions).

Impact of the device on aspects of daily living and satisfaction with device therapy: Subject response to a custom questionnaire to assess the impact of treatment with the device on subject's daily activities and satisfaction with the device.

CONFIDENTIAL DOCUMENT
This document contains confidential information, which is the property of Smith & Nephew, Inc. Do not copy, disclose, or circulate without written authorization from the appropriate Smith & Nephew personnel

SAFETY: Recording of AE associated with the target ulcer and all SAE

PK: NA

Adverse Device Effects:

Both volunteered and elicited

Other:

CONFIDENTIAL DOCUMENT
This document contains confidential information, which is the property of Smith & Nephew, Inc. Do not copy, disclose, or circulate without written authorization from the appropriate Smith & Nephew personnel

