This document contains confidential information, which is the property of Smith & Nephew, Inc. Do not copy, disclose, or circulate without written authorization from the appropriate Smith & Nephew personnel

CONFIDENTIAL DOCUMENT
This document contains confidential information, which is the property of Smith & Nephew, Inc. Do not copy, disclose, or circulate without written authorization from the appropriate Smith & Nephew personnel.

5. Remove NPWT topical dressing to assess the target ulcer.
6. Assess level of pain, post NPWT dressing removal, using the VAS.
7. Complete reason for dressing change assessment and record any additional dressing changes since previous assessment as an unscheduled visit.
8. Assess target ulcer and record if target ulcer is closed or if target ulcer is ready for and will be surgically closed.

Note 1: If the target ulcer is closed, skip procedures 9-15 and complete procedure 16.

Note 2: If target ulcer is ready for and will be surgically closed, skip procedures 9-16 and complete procedure 17.

9. Examine the ulcer for evidence of infection, and treat the infection as appropriate per local protocol.
10. Debride the ulcer if indicated, at the discretion of the Investigator.
11. If the target ulcer remains open, photograph and determine the post-debridement ulcer area (cm²), perimeter (cm), greatest depth (mm), volume (cm³), and maximum linear dimension (cm) using the ARANZ Silhouette wound imaging and measurement device if applicable.

If debridement is not performed, an image of the target ulcer is still required to determine the ulcer area (cm²), perimeter (cm), greatest depth (mm), volume (cm³) and maximum linear dimension (cm) using the ARANZ Silhouette wound imaging and measurement device.

12. Conduct an ulcer assessment using the modified Bates-Jensen wound assessment tool and record percentage tissue type/condition of peri-wound skin assessment (Normal, Erythematous, Edematous, Eczematous, Excoriated, Macerated, Indurated).
13. Re-application of investigational product (PICO) or comparator tNPWT system

according to randomization schedule.

Record any additional dressings used and rationale for using this dressing.

Type of wound filler dressing if used (foam or gauze-based filler dressing).

Number of personnel used to apply NPWT system.

Time used to apply NPWT system (minutes).

Record level of negative pressure, intensity setting and delivery mode selected for tNPWT subjects, if appropriate for device selected.

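### SAP derived variable 31 scores additional interventions from unscheduled visits, not from the admissions, complication surgery and referrals that the protocol names, and leaves some subjects with no value

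*SAP*

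**What the plan says.** The protocol synopsis lists additional interventions among the exploratory variables and defines them: "The number of subjects that require hospital admission, a surgical intervention for a wound related complication, or specialist referral for wound related complication". The data are requested at Study Visits 2-12 (Protocol 9.1.4, step 2), and in the same terms at Visits 13 and 14 (9.1.5 and 9.1.6): "subjects will be queried as to any additional ulcer-related interventions requiring hospital admission, surgical intervention or specialist referral since the last assessment".

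SAP 4.3 does not refer to those events. The condition for Yes in derived variable 31 is "If an unscheduled visit is recorded, where the reason for intervention is not given as routine". The only other branch is "If no unscheduled visits are recorded: Intervention = No". Variable 33 then combines variable 31 with antibiotic use (variable 32): Yes if either is Yes, No if either is No. SAP 4.11 compares the arms by Fisher's exact test on the combination and on each part separately.

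The protocol determines what becomes an unscheduled visit. Section 9.1.7 says "Subjects using a negative pressure filler dressing or using tNPWT will be instructed to complete a dressing change in 2-3 days from application" and adds "This visit should be captured as an unscheduled visit". Step 7 of 9.1.4 also has sites "record any additional dressing changes since previous assessment as an unscheduled visit". Protocol 6.2 makes a filler optional with PICO.

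**The concern.** The variable to be tested and the endpoint in the protocol describe different things. One is an unscheduled visit with a certain label; the other is a clinical event that sites already ask about. No other derived variable in SAP 4.3 captures admission, complication surgery or referral, so the protocol's endpoint has no derivation.

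The number of unscheduled visits depends on the device and on filler use, so misclassification need not be equal in the two arms. A difference in the Fisher test could then reflect how dressing changes are scheduled and labelled. Protocol 9.5 adds a consequence: a statistical difference in any exploratory assessment leads to a post-hoc health economic analysis, and additional interventions are among the resource items it lists.

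**Working it through.** The documents give no rate or power for this endpoint, so there is no planned figure to reproduce. Steps 1 and 2 compare texts. Steps 3 to 6 are illustrations under stated assumptions.

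**1. Variable 31 against the protocol definition**

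| Subject's records | Protocol definition | Variable 31 |
|---|---|---|
| No unscheduled visit, no event | No | No |
| No unscheduled visit; admission or referral reported at a scheduled visit | Yes | No |
| Only routine unscheduled visits, no event | No | no value |
| Only routine unscheduled visits; admission or referral reported at a scheduled visit | Yes | no value |
| A non-routine unscheduled dressing change, no event | No | Yes |
| A non-routine unscheduled visit and an event | Yes | Yes |

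The two agree in the first and last rows only. If sites label planned changes as routine, the third row is the expected state of an uneventful tNPWT subject.

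**2. Variable 33**

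A subject with Yes on one component and No on the other meets both branches. A subject with no value on variable 31 takes the value of the antibiotic variable alone.

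**3. Planned unscheduled visits over 12 weekly intervals**

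- tNPWT, one change at 2-3 days per interval: 12 × 1 = 12.
- tNPWT, if no dressing exceeds the 3-day limit in SAP 4.6: a 7-day interval needs three dressings, so two changes between visits, 12 × 2 = 24.
- PICO with filler: the same instruction as tNPWT.
- PICO without filler on a low-exuding wound: none instructed (7-day limit, Protocol 6.2).

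**4. False Yes scores in the tNPWT arm**

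Assume that a share q of the planned visits carries a non-routine label without any event, that visits are independent, and that all subjects complete 12 weeks. Then P(at least one) = 1 − (1 − q)^m.

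| q | m = 12 | m = 24 |
|---|---|---|
| 0 | 0 | 0 |
| 0.5% | 5.8% | 11.3% |
| 1% | 1 − 0.99^12 = 11.4% | 21.4% |
| 2% | 1 − 0.98^12 = 21.5% | 38.4% |

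Next take 80 subjects per arm (Protocol 11), an assumed true event rate of 10% in both arms, and a share f of PICO subjects with filler. With s the probability above, the scored rates are 1 − 0.9(1 − s) for tNPWT and 1 − 0.9(1 − f·s) for PICO. For q = 1%, m = 12 and f = 0 they are 20.2% and 10.0%. The exact probability that a two-sided 5% Fisher test rejects (m = 12 / m = 24) is:

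| q | f = 0 | f = 0.5 |
|---|---|---|
| 0.5% | 12% / 36% | 5% / 10% |
| 1% | 36% / 84% | 10% / 24% |
| 2% | 85% / >99% | 24% / 57% |

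If all PICO subjects use filler, the probability stays near 3%. If the variable is derived from the events themselves, it is 1.6%, 2.8% and 3.0% at true rates of 5%, 10% and 15%.

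**5. The opposite direction**

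Step 4 allows no mislabelled visits for PICO without filler, so it can only point one way. Protocol 4.2 reports a mean PICO wear time of 4.6 days in a 20-patient study of mixed wounds. Over 84 days that is 84 / 4.6 = 18.3 dressings. Less the 12 applied at Study Visits 1-12, about 6 changes fall between visits. These are not instructed, so a higher non-routine share is plausible. At an assumed 5%, 1 − 0.95^6 = 26.5% of such PICO subjects would be scored Yes, more than the 11.4% for tNPWT at q = 1% and m = 12.

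**6. Subjects with no value**

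Suppose every planned change is labelled routine, every tNPWT subject has at least one, PICO subjects have none, and 10% of each arm has a non-routine visit (0.10 × 80 = 8). In the tNPWT arm 8 subjects are Yes and 80 − 8 = 72 have no value. Coding those as No gives 8/80 against 8/80. Treating them as missing gives 8/8 against 8/80. The SAP does not say which applies.

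**The case against.** The strongest reply is that the routine exclusion exists to remove the planned 2-3 day changes. If sites label all of them routine, q = 0 and they add no false Yes scores. That stands, and it makes any inflation conditional. It does not rescue the rule: neither document defines routine, and correct labelling moves uneventful tNPWT subjects into the group with no value.

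A reader might infer that the rule favours PICO, or that the Fisher test would in effect compare visit frequency. The documents do not support either. Any additional dressing change is recorded as an unscheduled visit in both arms. Protocol 6.2 limits the PICO kit to 6 days on moderately exuding wounds, less than the 7-day visit interval. Filler use is not given, and step 5 shows that the direction can reverse.

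Other points also have weight. The CRF is not available here, and the field for the reason for intervention may include admission, surgery or referral among its options. Even so, variable 31 accepts any non-routine reason and needs an unscheduled visit. Protocol 9.4 leaves the need for additional interventions to the investigator's opinion, so the protocol is not uniform, but that wording does not point to unscheduled visits either. Admissions are not lost to the report, because hospitalization makes an event serious (Protocol 12.2) and serious events are summarized by arm (SAP 4.13). That does not correct this variable.

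**Conclusion.** The concern holds as a definitional error. Variable 31 does not measure the protocol's additional interventions. It counts non-routine dressing changes, misses admissions and referrals reported only at a scheduled visit, and gives no value to subjects whose unscheduled visits are all routine. These conclusions follow from the texts and need no assumption.

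The subjects without a value, and any mislabelling, can differ by arm, because instructed 2-3 day changes apply to all tNPWT subjects but only to PICO subjects with a filler. The direction and size of any resulting bias cannot be established. The 11.4% and 21.5% figures, and the Fisher probabilities built on such rates, rest on assumed labelling rates, independent visits and a full 12 weeks of treatment, although treatment stops at closure.

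The endpoint is exploratory. The primary and secondary conclusions are unaffected. The rule should still be corrected, because it feeds formal comparisons between arms.

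**What to change.** - **Variable 31.** Set Intervention = Yes if a hospital admission, surgery for a wound-related complication (not planned surgical closure), or specialist referral for a wound-related complication is recorded at any post-baseline visit. Set No for all other subjects with follow-up. State whether an admission must be ulcer-related: the visit query says so, the synopsis does not.
- **Unscheduled dressing changes.** Report them by arm, routine and non-routine, as separate descriptive items, and define routine.
- **Variable 33.** Replace *or* by *and* in the No branch. Make this change together with the one to variable 31; made alone, it would pass the missing values on to the combination.

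The cost is mainly SAP wording, since the protocol already has sites query these events. One check is needed: the query asks about surgical intervention in general, so confirm that the CRF separates complication surgery from planned closure. If it does not, those records need review before analysis.
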